6.2. PREPARATION/HANDLING/STORAGE/ACCOUNTABILITY

6.2.1. ACQUISITION AND ACCOUNTABILITY

All investigational product will be shipped to OMRC by AbbVie. Each supplied syringe will contain either 150 mg of risankizumab or a matching placebo will be administered to patients at OMRC by an unblinded pharmacist at OMRC. All patients as well as physicians performing efficacy and safety assessments will be blinded to the treatment group (600 mg or 300 mg) during the initial 52-week period. Used syringes will be placed in sharps containers. The unblinded pharmacist will keep a record of administered drug.

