1.3. SCHEDULE OF ACTIVITIES (SOA)

1.3 SCHEDULE OF ACTIVITIES (SOA)

	Day -28 to Day -1	Day 0/BL/Wk 0	Day 14/Wk 2	Day 28/Wk 4	Day 56/Wk 8	Day 84/Wk 12	Day 112/Wk 16	Day 154/Wk 22	Day 196/Wk 28	Day 238/Wk 34	Day 280/Wk 40	Day 322/Wk 46	Day 364/Wk 52	Day 406/Wk 58	Day 448/Wk 64	Day 490/Wk 70	Day 532/Wk 76	Day 574/Wk 82	Day 616/Wk 88	Day 658/Wk 94	Day 700/Wk 100 /Early Disc
Visit window	Plus or minus 7 days																				
Interviews and Questionnaires																					
Subject information and informed consent	✓																				
Eligibility criteria	✓	✓																			
Medical history	✓																				
Psoriasis history	✓																				
Demographics	✓																				
Drug, tobacco (including e-cigarettes), and alcohol history	✓																				
AE assessment	✓	✓	✓	✓	✓	✓	✓	✓	✓	✓	✓	✓	✓	✓	✓	✓	✓	✓	✓	✓	
Prior/concomitant therapy	✓	✓	✓	✓	✓	✓	✓	✓	✓	✓	✓	✓	✓	✓	✓	✓	✓	✓	✓	✓	
TB screening	✓																				
Patient Reported Outcomes (DLQI)		✓							✓			✓									
Suicidal thoughts or actions screening (CSSRS)	✓																				
Labs and Examinations																					
Height	✓																				
Vital signs	✓	✓	✓	✓	✓	✓	✓	✓	✓	✓	✓	✓	✓	✓	✓	✓	✓	✓	✓	✓	
Complete physical examination	✓	✓		✓				✓												✓	
Targeted physical examination			✓		✓	✓	✓		✓	✓	✓	✓	✓	✓	✓	✓	✓	✓	✓		
Urine pregnancy test (females of childbearing potential only)	✓	✓		✓		✓	✓		✓	✓	✓	✓	✓	✓	✓	✓	✓	✓	✓		
TB test (QuantiFERON-TB Gold test) 4mL/0.8 teaspoon of blood		✓																			
HIV, HBV, and HCV screening 8mL/1.6 teaspoons of blood		✓																			

KNOCKOUT STUDY

	Day -28 to Day -1	Day 0/BL/Wk 0	Day 14/Wk 2	Day 28/Wk 4	Day 56/Wk 8	Day 84/Wk 12	Day 112/Wk 16	Day 154/Wk 22	Day 196/Wk 28	Day 238Wk 34	Day 280/Wk 40	Day 322/Wk 46	Day 364/Wk 52	Day 406/Wk 58	Day 448/Wk 64	Day 490/Wk 70	Day 532/Wk 76	Day 574/Wk 82	Day 616/Wk 88	Day 658/Wk 94	Day 700/Wk 100 /Early Disc
Visit window	Plus or minus 7 days																				
Hematology, clinical chemistry, and urinalysis 8mL/1.6 teaspoons of blood	✓			✓	✓			✓				✓									
PASI	✓	✓	✓	✓	✓	✓	✓	✓	✓	✓	✓	✓	✓	✓	✓	✓	✓	✓	✓	✓	
BSA	✓	✓	✓	✓	✓	✓	✓	✓	✓	✓	✓	✓	✓	✓	✓	✓	✓	✓	✓	✓	
sPGA	✓	✓	✓	✓	✓	✓	✓	✓	✓	✓	✓	✓	✓	✓	✓	✓	✓	✓	✓	✓	
Skin biopsies (6-mm punch samples)		✓										✓									
Treatment																					
Randomization/drug assignment		✓																			
Administer study drug to subjects		✓		✓			✓														
In-clinic post-dose monitoring (30 minutes)		✓		✓				✓													

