3. OBJECTIVES AND ENDPOINTS

OBJECTIVES	ENDPOINTS	JUSTIFICATION FOR ENDPOINTS

Primary Objective: to determine whether the reduction in the number and/or effector function of epidermal CD8+CD103+ Trm cells at Week 52 (compared to baseline numbers) in psoriasis patients treated with 4X standard induction doses of risankizumab (600 mg at Weeks 0, 4, and 16) is greater when compared to psoriasis patients treated with 2X standard induction doses of risankizumab (300 mg at Weeks 0, 4, and 16).
	
Primary Endpoint: change from baseline in number and/or effector function of epidermal CD8+CD103+ Trm cells at Week 52 in psoriasis patients treated with 4X standard induction doses of risankizumab (600 mg at Weeks 0, 4, and 16) or 2X standard induction doses of risankizumab (300 mg at Weeks 0, 4, and 16).
	
Trm cells are the primary cells within psoriatic lesions (and healed skin) that are responsible for psoriasis recurrences after skin lesions have cleared. Targeting these cells, as proposed here, may lead to prolonged remission of psoriasis.

Secondary Objectives:
 
 1) to compare the percentage of patients with PASI 100 (complete clearance) at Weeks 28, 40, 52, and 100 in patients receiving 4X standard induction doses of risankizumab vs. those receiving 2X standard induction doses of risankizumab and 2) to compare safety events over 100 weeks in patients receiving 4X standard induction doses of risankizumab vs. those receiving 2X standard induction doses of risankizumab. 	
Secondary Endpoints:
 
 1) PASI 100 (complete clearance) response at Weeks 28, 40, 52, and 100 in patients receiving 4X standard induction doses of risankizumab or those receiving 2X standard induction doses of risankizumab and 2) safety events over 100 weeks in patients receiving 4X standard induction doses of risankizumab or those receiving 2X standard induction doses of risankizumab. 	
These are standard measures of efficacy and safety for psoriasis studies.

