4. STUDY DESIGN

4.1. OVERALL DESIGN

The overall hypothesis for this study is to determine whether high-dose risankizumab, an anti-IL-23 blocker approved for plaque psoriasis, can target Trm cells with psoriatic lesions, and whether a more marked reduction of Trm cells correlates with high levels of efficacy and longer periods of disease remission.

In summary, this is single-center, randomized, interventional, Phase 2 study (KNOCKOUT) consisting of a 52-week double-blind period followed by a 48-week unblinded extension comparing tissue and clinical effects of 4X standard induction doses of risankizumab vs. 2X standard induction doses of risankizumab in patients with moderate-severe plaque psoriasis.

Twenty patients with moderate to severe plaque psoriasis will be randomized in a 1:1 manner to receive either risankizumab 600 mg (4X dosing) or 300 mg (2X dosing), SC, at Weeks 0, 4, and 16. All patients will receive four SC injections at Weeks 0, 4, and 16 (into right arm, left arm, right thigh, left thigh) by an unblinded pharmacist. For patients randomized into the highest induction dose arm, each shot will contain 150 mg of risankizumab; for patients randomized into the 2X induction dose arm, two shots will contain 150 mg of risankizumab each and 2 shots will contain placebo (sterile saline).

Skin biopsies of lesional and/or non-lesional skin will be obtained at Week 0, and an additional skin biopsy of lesional skin will be obtained at Week 52. These samples will be processed for immunohistochemical staining and RNA seq analysis. Psoriasis severity clinical assessments (PASI, sPGA, BSA) and safety assessments (vital signs, history) will be assessed at screening and Weeks 0, 2, 4, 8, 12, 16, 22, 28, 34, 40, 46, 52, 58, 64, 70, 76, 82, 88, 94, and 100 (to assess secondary and additional endpoints). Routine labs will be performed at Screening and at Weeks 4, 8, 22, and 52.

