6.3. MEASURES TO MINIMIZE BIAS: RANDOMIZATION AND BLINDING

To avoid unblinding of the patients and investigators as to treatment status during the double-blind period, all patients will be given 4 shots at Weeks 0, 4, and 16. An unblinded pharmacist will prepare and subcutaneously administer all drug and placebo (i.e., investigational product IP) to patients. This person will also be charged with accepting all IP shipments from AbbVie, storing IP in a locked refrigerator (maintained at 2-8 °C), and recording all IP administrations to patients. IP will be delivered in the right arm, left arm, right thigh, and left thigh by the unblinded pharmacist at Weeks 0, 4, and 16. Monitoring will occur for 30 minutes post-dose. Patients will be shielded from viewing injections performed by the unblinded pharmacist. If an investigator believes the safety of a study subject is at risk due to study drug administrations, that investigator may unblind the treatment status to help direct/coordinate medical care of that patient.

Once a subject reaches the end of the initial 52-week double blind period, the investigators, study staff and subject will be unblinded as to the treatment group.

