8. STUDY ASSESSMENTS AND PROCEDURES

8.1. EFFICACY ASSESSMENTS

Clinical Assessments

All assessments will be performed at Oregon Medical Research Center, P.C. At screening, Week 0, Week 2, Week 4, and every visit thereafter until Week 100, the following will be done:

1. Physical examination (*complete exam at screening, baseline, Week 4, Week 16, and Week 52; targeted exam at every other visit per Investigator discretion)
2. Psoriasis Area and Severity (PASI)
3. Body Surface Area (BSA)
4. Static Physician's Global Assessment (sPGA)
5. DLQI (*at Weeks 0, 28, and 52 only)
6. Vital signs (temperature, blood pressure, heart rate, respiratory rate, and weight)
7. Past medical history, including past systemic treatments for psoriasis (*at screening visit only)
8. Columbia Suicide Severity Rating Scale (*at screening visit only)
9. Interim health history to assess for possible adverse events (*at all visits following the baseline visit)

Laboratory Assessments

At screening, Weeks 4, 8, 22, and 52, the following will be collected at Oregon Medical Research Center, P.C. and sent to a local laboratory:

1. Complete blood count (CBC) w/differential
2. Comprehensive metabolic panel
3. Urinalysis
4. Urine pregnancy test (*performed on-site only for women of child-bearing potential, at each visit up to Week 52, except Week 2)

At screening only, the following will be collected at Oregon Medical Research Center, P.C. and sent to a local laboratory:

1. HIV antibody
2. Hepatitis B panel
3. Hepatitis C antibody
4. Quantiferon Gold

At Weeks 0 and 52, the following will be collected at Oregon Medical Research Center, P.C. and shipped to the laboratory of [name] at the University of Michigan:

1. One 6 mm skin biopsy of lesional skin (at Weeks 0 and 52) and one 6 mm skin biopsy of peri-lesional skin (at Week 0); both will be bisected and processed as follows:

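### The treatment code opens at Week 52, as the second primary-endpoint biopsy is taken and before it is read, and no stated rule keeps the laboratory or the analysts masked

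*Combined protocol and SAP*

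**What the plan says.** **Who is blinded.** Section 6.2.1 states "All patients as well as physicians performing efficacy and safety assessments will be blinded to the treatment group (600 mg or 300 mg") and limits this to the initial 52 weeks. Section 6.3 gives the purpose of the four-injection scheme as "To avoid unblinding of the patients and investigators as to treatment status during the double-blind period".

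**When the code opens, and to whom.** Section 6.3 sets a rolling rule. It takes effect "Once a subject reaches the end of the initial 52-week double blind period". What follows for that subject is that "the investigators, study staff and subject will be unblinded as to the treatment group". The trigger is the individual subject's progress. It is not the last subject's Week 52 visit, completion of the biopsy reads or a data lock.

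**What the primary endpoint is.** Section 3 defines it as "change from baseline in number and/or effector function of epidermal CD8+CD103+ Trm cells at Week 52". Section 4.1 adds that "an additional skin biopsy of lesional skin will be obtained at Week 52", and Section 8.1 says "At Weeks 0 and 52, the following will be collected at Oregon Medical Research Center, P.C. and shipped to the laboratory" at a university. There the tissue is sequenced, stained, imaged, segmented and clustered.

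**Who analyses it.** Section 9.1 assigns the statistical analysis to the funder's statistics group, and Section 9.6 plans a between-arm t-test on the change at Week 52. Section 10.1.2 says research data are identified by a study number.

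**The concern.** The blind ends where the primary measurement begins. It covers the clinical scores (PASI, sPGA, BSA) up to Week 52, but these are secondary or additional endpoints. The one primary endpoint depends on tissue taken when the code opens and on laboratory work that comes later.

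That work leaves room for judgement:

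- The synopsis allows a lesional sample at Week 52 to come from a current lesion or from a formerly affected area, so someone picks the site.
- Section 8.1 has cells filtered, batch-corrected, assigned to types, segmented and clustered, with no cell-calling threshold or cluster-labelling rule fixed in advance.
- The endpoint leaves open whether cell count, cell function or both will carry the result.

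If people making these choices know the arm, the 4X versus 2X difference could be biased in either direction. The trial's double-blind label would then not describe its primary result.

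**Working it through.** The plan gives no figure on this point to reproduce, so the check sets the sections side by side.

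**1. Order of events at Week 52.** The schedule of activities puts Week 52 at Day 364 (52 × 7) and gives a visit window of "Plus or minus 7 days". The visit can therefore fall from Day 357 (364 − 7) to Day 371 (364 + 7). Section 6.3 does not say whether the end of the period means the calendar day or the visit.

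- If it means Day 364, a visit after that day puts the biopsy after unblinding. An early visit leaves at most 7 days between biopsy and code opening.
- If it means the visit, the order of biopsy, clinical scoring and unblinding within the visit is not stated.

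Neither reading guarantees that the site is chosen and the biopsy taken while the code is closed. The same gap affects Week 52 PASI 100, a secondary endpoint.

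**2. Order of code opening and reading.** Processing must follow collection. Section 8.1 stores the cryopreserved half at −80 °C until it is shipped and processed. It gives no dates for work on the formalin-fixed half. Apart from the possible interval of up to 7 days in step 1, the Week 52 tissue is read at or after the point where that subject's code has been opened to the site.

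**3. Who is masked, role by role.**

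| Role | Until Week 52 | After Week 52 |
|---|---|---|
| Subject | Blinded (6.2.1, 6.3) | Unblinded (6.3) |
| Investigators and assessing physicians | Blinded (6.2.1, 6.3) | Investigators unblinded (6.3) |
| Study staff | Blinded by implication (6.3) | Unblinded (6.3) |
| Pharmacist giving the injections | Unblinded by design | Unblinded |
| University laboratory and bioinformatics team | Not stated | Not stated |
| Funder's statisticians | Not stated | Not stated |

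If laboratory personnel count as study staff, Section 6.3 unblinds them at Week 52. If they do not, no available rule covers them. Neither case protects the readout.

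**4. Does the study number close the gap?** Section 10.1.2 presents it as a confidentiality measure. It hides the person. It does not hide the arm from anyone who holds, or is told, the link between number and treatment, and from Week 52 the site holds that link.

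**5. Extent.** Twenty subjects are randomized 1:1, so 10 per arm. Each has one planned Week 52 lesional biopsy, which makes up to 20 of 20 Week 52 primary samples exposed. Withdrawals would reduce the number, since Section 7.1 does not replace them.

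**6. Size of bias.** The documents give no standard deviation, expected difference or reader-error figure for the Trm endpoint. No bias in cells, in standard deviations or in error rate can be derived, and none is offered here.

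**The case against.** The strongest reply is that the protocol is silent on these roles and does not open the code to them. Section 6.2.1 is an accountability section and does not claim to list every blinded role. Elsewhere staff means site staff (Sections 10.1.2 and 10.1.5), the laboratory is external, data travel under a study number, and no section sends treatment codes to it. Section 1.2 counts Week 52 as part of the double-blind period, so the biopsy may well come first. Much of the pipeline is software-driven, with automated segmentation and unsupervised clustering. Section 9 calls the study exploratory and descriptive.

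Much of this stands, and it limits the point. A reader might infer any of the following, and the documents support none of them:

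- **That the laboratory will read the samples unblinded.** No text says so.
- **That only patients and physicians are ever blinded.** Section 6.3 also covers investigators and implies that study staff are blinded until Week 52.
- **That marker staining, including CD103, is tuned after codes open.** Section 8.1 says it will be optimised but gives no date, so it could be done earlier.

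A masking rule may also exist in the SAP to which Section 9.1 refers, or in Section 10.1.4. Neither was available in the text examined.

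The reply does not supply protection. A rolling unblinding rule is written down, and no available rule stops the code at the laboratory door. Cluster naming and segmentation settings still need judgement, and Section 9.6 still compares the arms on this endpoint.

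**Conclusion.** The point holds as an unprotected risk. The stated double-blind does not extend to the reading and analysis of the Week 52 biopsy, and no available text puts that biopsy ahead of unblinding. Up to 20 of 20 Week 52 primary samples are affected, and the amount of bias cannot be determined.

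The conclusion rests on two assumptions: that codes are opened promptly under Section 6.3, and that no masking rule for the laboratory or analysts stands in the text not available. If such a rule exists, Sections 6.2.1 and 6.3 need only cite it. The exploratory purpose lowers the stakes but does not remove them, because this is the primary between-arm comparison of a trial described as double-blind.

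**What to change.** Add to Sections 6.2.1 and 6.3:

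1. At Week 52, the choice of biopsy site, the biopsy itself and the clinical assessments are completed before that subject's code is opened.
2. Samples go to the laboratory under a code that does not reveal the arm. Laboratory, bioinformatics and statistical staff receive no treatment codes until staining thresholds, segmentation settings and cluster labels are fixed and the Week 52 Trm data are locked.

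Site staff and subjects can still be unblinded at Week 52 as planned. No extra reader, visit or procedure is needed. The cost is about a paragraph of text, a documented code-release step and a later first look at Trm results by arm.

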6.2.2. FORMULATION, APPEARANCE, PACKAGING, AND LABELING

SKYRIZI (risankizumab-rzaa) injection 150 mg/mL prefilled syringe and prefilled pen contain a sterile, preservative-free, colorless to yellow, and clear to slightly opalescent solution. Each single-dose prefilled syringe or prefilled pen consists of a 1 mL glass syringe with a fixed 27- gauge $\frac{1}{2}$ inch needle with needle guard.

A copy of the drug labels prepared for this study are provided with this protocol for reference.

6.2.3. PRODUCT STORAGE AND STABILITY

Investigational product will be stored at 4 °C (2-8 °C range), in the original carton to protect from light, and in a locked and temperature-controlled refrigerator, one that only can be accessed by the unblinded pharmacist.

6.2.4. PREPARATION

Risankizumab injections will be prepared and administered in the clinic according to dosing instructions per the IB.

- Before injecting, remove the carton with SKYRIZI from the refrigerator and without removing the prefilled pen or prefilled syringe(s) from the carton, allow SKYRIZI to reach room temperature out of direct sunlight (30 to 90 minutes for the prefilled pen and 15 to 30 minutes for the prefilled syringe(s)).
- Visually inspect SKYRIZI for particulate matter and discoloration prior to administration.
 - SKYRIZI 150 mg/mL is a colorless to yellow and clear to slightly opalescent solution. SKYRIZI 75 mg/0.83 mL is a colorless to slightly yellow and clear to slightly opalescent solution.
 - The solution may contain a few translucent to white particles. Do not use if the solution contains large particles or is cloudy or discolored.

6.3. MEASURES TO MINIMIZE BIAS: RANDOMIZATION AND BLINDING

To avoid unblinding of the patients and investigators as to treatment status during the double-blind period, all patients will be given 4 shots at Weeks 0, 4, and 16. An unblinded pharmacist will prepare and subcutaneously administer all drug and placebo (i.e., investigational product IP) to patients. This person will also be charged with accepting all IP shipments from AbbVie, storing IP in a locked refrigerator (maintained at 2-8 °C), and recording all IP administrations to patients. IP will be delivered in the right arm, left arm, right thigh, and left thigh by the unblinded pharmacist at Weeks 0, 4, and 16. Monitoring will occur for 30 minutes post-dose. Patients will be shielded from viewing injections performed by the unblinded pharmacist. If an investigator believes the safety of a study subject is at risk due to study drug administrations, that investigator may unblind the treatment status to help direct/coordinate medical care of that patient.

Once a subject reaches the end of the initial 52-week double blind period, the investigators, study staff and subject will be unblinded as to the treatment group.

6.4. STUDY INTERVENTION COMPLIANCE

6.5. CONCOMITANT THERAPY

6.5.1. RESCUE MEDICINE

No rescue medications or concomitant therapies for psoriasis will be allowed in this study.

7. STUDY INTERVENTION DISCONTINUATION AND PARTICIPANT DISCONTINUATION/WITHDRAWAL

7.1. DISCONTINUATION OF STUDY INTERVENTION

Subjects will be withdrawn from the study if, according to the investigator, safety of the subjects is compromised in any manner, or if subjects are no longer able to comply with study visits and procedures. Study subjects who are withdrawn will follow-up with their referring dermatologist, when possible. Study subjects who are withdrawn will not be replaced.

The reason for withdrawal will be captured in the Case Report Form (CRF).

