- currently have an infection or if you have an infection that keeps coming back.
- have TB.
- have recently received or plan to receive an immunization (vaccine); you should not be given certain types of vaccines while using risankizumab.

Injection Site Reactions: Injection of study drug under the skin could result in redness, pain, swelling, or hardness at the site of the injection. Also, bleeding or bruising at the injection site may occur. Most injection site reactions are not severe and resolve without any treatment, but can be uncomfortable for a few hours to a few days.

Liver Disease: A serious adverse reaction of drug-induced liver injury in conjunction with a rash that required hospitalization was reported in a patient with Crohn's disease following two 600 mg intravenous doses of risankizumab. The liver test abnormalities resolved following administration of steroids. Risankizumab was subsequently discontinued. Patients with liver cirrhosis should not be treated with risankizumab. During risankizumab treatment, prompt investigation of the cause of liver enzyme elevation is recommended to identify potential cases of drug-induced liver injury. Stopping treatment is recommended, if drug-induced liver injury is suspected. Patients should seek immediate medical attention if they experience symptoms suggestive of liver disease.

Other Possible Risks:

Some drugs that affect the immune response have been associated with side effects such as serious allergic reactions, and possible increased risk of malignancy (cancer).

Allergic Reactions: All drugs have a potential risk of an allergic reaction. Allergic reactions may vary from mild (rash, hives, itching) to severe reactions such as anaphylaxis (which may include difficulty breathing, swelling of the face or throat, low blood pressure, or loss of consciousness). A severe allergic reaction requires immediate medical treatment and could result in permanent disability or death. It is important to tell your study doctor about any past allergic reactions that you may have had to other drugs including antibody drugs (which are usually given by IV or injection under the skin). If you seek medical care for a possible allergic reaction, please request the treating health care provider to contact the study physician. Serious hypersensitivity reactions, including anaphylaxis, have been reported with use of risankizumab.

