4.4. END OF STUDY DEFINITION

Patients will be observed for 100 weeks after their first dose of risankizumab (84 weeks after their last dose of risankizumab).

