9.3. ANALYSIS SET

The Full Analysis Set (FAS) includes all randomized subjects who received at least 1 dose of study drug. The FAS will be used for all efficacy and Baseline analyses. Subjects will be grouped according to treatment as randomized.

The Safety Analysis Set consists of all subjects who received at least 1 dose of study drug. For the Safety Analysis Set, subjects are assigned to a treatment group based on the treatment actually received, regardless of the treatment randomized.

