9.4. HANDLING OF POTENTIAL INTERCURRENT EVENTS

There will be two major types of intercurrent events (ICE) in this study: risankizumab discontinuation due to lack of efficacy or intolerance, and risankizumab discontinuation due to other reasons. Each intercurrent event will be addressed by different strategies, specifically:

Table ** Handling of Potential Intercurrent Events

Intercurrent Event	Strategy	Description
risankizumab or study discontinuation due to lack of efficacy or intolerance	Composite variable strategy	Data after risankizumab or study discontinuation due to lack of efficacy or intolerance will be set to non-responder for binary endpoints. For continuous endpoints, set to last observation before discontinuation.
risankizumab discontinuation due to other reasons	Treatment policy strategy	Data after risankizumab discontinuation due to other reasons will be used regardless of whether the intercurrent event occurs.

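### Section 7.1 answers a judged safety problem only with withdrawal from the study, even in the 84 weeks after the last dose, so the safety event itself ends that subject's 100-week safety observation

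*Combined protocol and SAP*

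**What the plan says.** Section 7.1 concerns discontinuation of the intervention, but the action it states is removal from the study: "Subjects will be withdrawn from the study if, according to the investigator, safety of the subjects is compromised in any manner". Inability to comply with visits has the same result. Withdrawn subjects are sent to their referring dermatologist where that is possible, and they are not replaced. Section 7.2 covers only withdrawal at the participant's own request.

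Other sections touch on the subject:

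- Section 4.4: "Patients will be observed for 100 weeks after their first dose of risankizumab (84 weeks after their last dose of risankizumab".
- Section 3 makes the comparison of safety events over 100 weeks a secondary objective.
- Section 2.3.1, on liver injury: "Stopping treatment is recommended, if drug-induced liver injury is suspected". It does not mention leaving the study.
- Section 6.3: an investigator worried about safety has a further option, "that investigator may unblind the treatment status to help direct/coordinate medical care of that patient".
- Section 9.4 treats stopping risankizumab and stopping the study as different things. For stopping drug for reasons other than lack of efficacy or intolerance, it says: "Data after risankizumab discontinuation due to other reasons will be used regardless of whether the intercurrent event occurs".
- Section 1.3 places an early discontinuation visit in the Week 100 column.
- Section 9.3: "The Safety Analysis Set consists of all subjects who received at least 1 dose of study drug".
- Section 9.8 closes the TEAE window 140 days after the last dose. It does not impute missing safety data. It gives SAEs, deaths and AEs leading to discontinuation as percentages and per 100 patient-years.

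**The concern.** Stopping a drug and stopping observation are separate decisions, and Section 7.1 merges them. After Week 16 there is no study drug left to stop. Withdrawal then frees the subject from the ban on psoriasis therapy in Section 6.5.1, but otherwise it mainly ends data collection.

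What is at stake is the 100-week safety comparison. If one arm has more events that the investigator judges to compromise safety, that arm is watched for less time, and the subjects lost are those whose later course matters most. Rates per 100 patient-years correct for unequal time only if leaving is unrelated to later risk. That is doubtful when a safety event is the reason for leaving.

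Follow-up has particular value here. Section 2.3.1 gives the highest repeated subcutaneous dose tested as 180 mg, and both arms exceed it at 300 mg and 600 mg. Repeated intravenous doses up to 1,200 mg have been given, which tempers the point. As an example, a subject withdrawn at Week 16 for raised liver enzymes would miss the scheduled Week 22 and Week 52 laboratory tests, apart from anything done at an early discontinuation visit or in outside care.

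**Working it through.** **Inputs.** Doses at Weeks 0, 4 and 16 (Section 6.1.2). Observation to Week 100 (Section 4.4). TEAE window of 140 days after the last dose (Section 9.8). Twenty subjects randomised 1:1, taken as 10 per arm (Section 6.1.2). Visits as listed in Section 4.1. The withdrawal weeks and counts below are assumptions, because the plan gives none.

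**The plan's own figure.** 100 − 16 = 84 weeks after the last dose, as Section 4.4 states.

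**TEAE window.** 140 / 7 = 20 weeks. After all three doses it closes at Week 16 + 20 = Week 36. If the last dose was at Week 4, it closes at Week 24.

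**Loss from one withdrawal at week w.** Observation lost = 100 − w weeks. Planned person-time per arm = 10 × 100 = 1,000 patient-weeks. Share lost = (100 − w) / 1,000. For a fully dosed subject, TEAE-window weeks lost = 36 − w, or zero from Week 36.

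| Withdrawal week | Weeks lost | Share of arm's person-time | TEAE-window weeks lost |
|---|---|---|---|
| 16 (after dosing) | 84 | 8.4% | 20 |
| 20 | 80 | 8.0% | 16 |
| 30 | 70 | 7.0% | 6 |
| 36 | 64 | 6.4% | 0 |
| 52 | 48 | 4.8% | 0 |

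A subject withdrawn at Week 16 without the third dose loses 24 − 16 = 8 weeks of the TEAE window.

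**Range by number of withdrawals in one arm at Week 16.** None: 0%. One: 84 / 1,000 = 8.4%. Two: 168 / 1,000 = 16.8%.

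**Visits.** After Week 16 the scheduled visits are Weeks 22, 28, 34, 40, 46, 52, 58, 64, 70, 76, 82, 88, 94 and 100, which is 14. A Week 16 withdrawal loses all 14, or 13 net if the early discontinuation visit is done. Eleven of the 14 (Weeks 40 to 100) fall after the TEAE window of a fully dosed subject.

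**Rough guide to frequency.** Suppose the 2.4% serious side effect rate in Section 2.3.1 were the safety-withdrawal rate. It is a different event, mainly at 150 mg, over a period not stated. Expected per arm: 10 × 0.024 = 0.24. Chance of none among 20: 0.976^20 = 0.615. Chance of at least one: 1 − 0.615 = 0.385. On this assumption zero is the most likely count.

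**Whether another section overrides Section 7.1.** Section 4.4 and the visit list in Section 8.1 set the general schedule and do not say what happens after a safety event. Section 9.4 decides how data are analysed and does not require that they be collected. Unblinding under Section 6.3 leaves follow-up unchanged. The early discontinuation column is a single visit. None of these keeps a subject in follow-up once Section 7.1 applies.

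**The case against.** The best answer is that continued observation is the plan's default. Section 4.4 promises 100 weeks without requiring that all doses be given, Section 2.3.1 speaks of stopping treatment rather than leaving the study, and Section 9.4 separates the two. The trigger is also the investigator's judgement, and an investigator could reasonably hold that observation visits after Week 16 compromise nobody's safety. This shows that the authors had drug-only stopping in mind. It does not remove the rule: once safety is judged compromised, the consequence in Section 7.1 is mandatory and open-ended.

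The limits on the consequences do stand. The subject remains in the Safety Analysis Set and earlier events count. A fully dosed subject withdrawn from Week 36 loses no TEAE time. For a withdrawal classed as intolerance, PASI 100 is already determined: "Data after risankizumab or study discontinuation due to lack of efficacy or intolerance will be set to non-responder for binary endpoints". The study is exploratory and unpowered (Sections 9.1 and 9.2).

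A reader might infer more than the documents support:

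- That every AE or SAE leads to withdrawal. The trigger is the investigator's judgement, not the event.
- That the triggering events drop out of the analysis. Section 9.3 keeps the subject in.
- That the safety comparison is biased in a known direction or by a known amount. Neither the number nor the arm of any withdrawals is given.
- That the handling of the Week 52 Trm biopsy must change too. For continuous endpoints in intolerance cases Section 9.4 says "For continuous endpoints, set to last observation before discontinuation". Whether that is the right choice is a separate estimand question, and keeping safety follow-up does not depend on it.

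**Conclusion.** The point holds with limited scope. As written, Section 7.1 ends observation because of a safety event, although 84 of the 100 weeks come after the last dose and safety over 100 weeks is a secondary objective. One withdrawal between Week 16 and Week 52 costs between 8.4% and 4.8% of an arm's planned person-time. This assumes 10 subjects per arm and that Section 7.1 is followed literally. The total effect depends on how many subjects are withdrawn for safety, which the plan does not say and which may be zero. The damage would be incomplete, informatively censored descriptive safety data, mostly outside the TEAE tables. No confirmatory test is at stake. This is a worthwhile, low-cost improvement; it does not invalidate the trial.

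**What to change.** Amend Section 7.1 so that:

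- a safety concern stops any remaining study drug, with that decision staying with the investigator;
- the subject is asked to continue the already scheduled AE, safety and PASI visits to Week 100, unless consent is withdrawn or a procedure would be unsafe;
- the date and reason for stopping drug are recorded separately from the date and reason for leaving the study;
- a subject who has stopped drug and then needs psoriasis therapy barred by Section 6.5.1 may receive it and remain in AE follow-up, with its start date recorded.

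The cost is a protocol amendment with IRB approval and a decision on re-consent, as the Statement of Compliance requires. No visits are added. AEs after other psoriasis therapy will be harder to attribute, which is why the start date is needed. Only subjects still enrolled at approval can benefit, and their number is not given. The case report form is not in the documents, so whether a new field is needed is unknown.
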